Scope	
This is a pivotal, multicenter, prospective, randomized, open-label controlled trial clinical trial that aims to evaluate the safety and effectiveness of the Colovac Colorectal Anastomosis Protection Device compared to the standard of care (diverting ostomy). Subjects are randomized 1:1 to standard of care treatment (control group) or Colovac device treatment (treatment group). Additionally, to assess any deployment challenges or technical difficulties, and capture any adverse events that occur during Colovac implantation, the study includes a run-in component that will include the first two Colovac subjects for the PI at each US site.
 
For the randomized component, this pivotal study aims to enroll a total of 342 patients (171 patients in the control group and 171 in the treatment group) at up to 15 sites in the US and up to 10 sites in the EU.
 
For the non-randomized run-in component of the study, a maximum of 30 subjects (2 subjects at each US site) will be enrolled. Additionally, European sites with no experience implanting the Colovac device will enroll 2 subjects per site in a European run-in component. However, the IDE sample size will not be increased for these OUS subjects as they will not be included in the randomized cohort.

Investigational Device	Colovac Colorectal Anastomosis Protection Device
Device manufacturer	
Contract Medical International GmbH (CMI), Germany [name] [name] [contact] Office

Expected study duration	
Enrollment: 8-12 months FU period: 12 months Total expected study duration: 20-24 months

Follow-up Visits	Daily while hospitalized, 9 Days, 1 Month, 3 Months, 6 Months, 9 Months and 12 Months
Sponsor	
US: SafeHeal Inc. [name] [name]
 
EU: SafeHeal SAS [name], [name]

Primary Objectives	
The primary study objectives are:
 
 1) To assess the safety of the Colovac device by comparing the rate of major complications, as defined in the protocol; and 
To assess the effectiveness of the Colovac device in reducing the stoma creation rate.

Primary Endpoints	
The primary safety endpoint is the rate of subjects with post-operative major complications within 12 months.
 
The primary effectiveness endpoint assessed for all subjects in the Colovac arm at 12 months is a clinically meaningful reduction in stoma creation rate.

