Attach the vacuum tube to the vacuum connector and the vacuum connector to the PFM Asept Drainage Line Set and drain bottles.

SafeHeal Vacuum Loss Alert System

The Vacuum Loss Alert System (Figure 11) is a single-patient use, non-sterile unit used in conjunction with vacuum drainage system (as described above). The System attaches to the vacuum bottles and provides caregivers with visual and auditory alerts when a bottle reaches a low level of vacuum. The System is intended for use in conjunction with the existing visual bottle vacuum indicator to allow for continuous vacuum monitoring. The System is indicated for use during patient recovery in hospital/hospital-like environments (e.g., patient hospital rooms). Please refer to the Instructions for Use of the Colovac device and the Instructions for Use of the Vacuum Loss Alert System for instructions on how to attach the Vacuum Loss Alert System to the vacuum drainage system. Although the SafeHeal Vacuum Loss Alert System is not part of the Colovac Device, it will be supplied to sites.

[figure not shown]

Figure 11: SafeHeal Vacuum Loss Alert System

Additional Device

The Hollister 9781 Horizontal Tube Attachment Device is not part of the Colovac Device and must be purchased separately. For the SAFE-2 clinical trial, the Sponsor will supply the Hollister 9781 Horizontal Tube Attachment Device to the investigator sites.

The vacuum drainage tubes are secured to the subject using an adhesive. To minimize subject discomfort due to tube movement, the Hollister 9781 Horizontal Tube Attachment Device (Figure 12), a sterile, flexible support with adhesive backing, will be supplied to study sites.

Please refer to the Hollister 9781 Horizontal Tube Attachment Device Instructions for Use for information on how to attach it to patient's skin.

Figure 12: Hollister 9781 Horizontal Tube Attachment Device

STUDY DESIGN

OVERALL STUDY DESIGN

This is a pivotal, multicenter, prospective, randomized, open-label controlled trial. A total of 342 randomized subjects (171 investigational and 171 control subjects) will be enrolled at up to 15 US sites and up to 10 EU sites. Note that no site may enroll more than 20% of the total study enrollment without prior Sponsor approval. Subjects will be randomized into a control arm or a treatment arm (1:1 randomization) once all eligibility criteria have been met.

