However, in rare cases of severe clinically significant and symptomatic AL (peritonitis) when a device is removed prior to Day 10, the subject may require emergent, surgical treatment. In this case, as the priority is to quickly treat the patient, the priority will be given to the examination and washout of the anastomosis, abdomen and pelvis to determine the extent of the infection and the necessary intervention. The retrieval of the device will be considered as one of the last tasks, once the patient is

stabilized. Thus, as the anastomosis will have been cleansed at the time of the endoscopic removal of the device, it will not always be possible to confirm diversion of the fecal stream by endoscopic evaluation. In these rare cases, an alternative method to confirm the diversion of fecal stream and allow the device effectiveness to be determined, the absence of fecal peritonitis, will be assessed.

As shown in Figure 17, all AL in the Colovac group will be assessed for relationship to the device and inclusion in the primary safety endpoint as a major complication. Similarly, as shown in Figure 18, all AL in the Standard of Care (Control) group will be assessed for inclusion in the primary safety endpoint as a major complication. Note that all AL complications will be included in the AE summary tables.

SAFE-2 Pivotal Study

Clinical study Protocol Overview

[figure not shown]

Figure 17: Anastomotic Leakage in Colovac Group by Grade, Device Relationship and Type of Complication

SAFE-2 Pivotal Study

Clinical study Protocol Overview

[figure not shown]

Figure 18: Anastomotic Leakage in Standard of Care Group by Grade and Type of Complication

STUDY POPULATION

All subjects will require low anterior colorectal resection for colorectal cancer with a planned diverting loop ileostomy. Additionally, subjects must meet all of the inclusion and none of the exclusion criteria to be enrolled in the study. A maximum of 30 non-randomized subjects (two subjects at each US site) will be enrolled in the run-in component of the study. A total of 342 subjects (171 in the control arm and 171 in the Colovac arm) will be enrolled in the randomized component of the study. At least 50% of the randomized subjects will be enrolled at US sites.

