An independent DSMB will assess the progress of the clinical investigation, the safety data and the critical performance endpoints, and recommend to the sponsor whether to continue, suspend, modify,

or terminate the clinical investigation. The DSMB will consist of a minimum of three (3) non-SafeHeal employed physicians that are not participating investigators for the study, including a DSMB chairperson. Other than receiving compensation from the sponsor for their time spent as DSMB members, DSMB members should have no other relationship with the CRO, sponsor or investigator that could impair the members' ability to objectively review study data.

An ad hoc meeting will be called to review the study safety if the CEC causality determinations of the criteria listed in Section 0 trigger any of the study stopping criteria listed above in **Table 8**.

The DSMB shall follow a formal Charter which incorporates stopping rules.

SUSPENSION OR PREMATURE TERMINATION

If the stopping rule included in the DSMB charter is met, the DSMB may recommend suspending or terminating the study. Additionally, if the Sponsor and/or the DSMB determine that the study presents an unacceptable risk, the study may be terminated. Termination shall occur not later than 5 working days after the sponsor and/or the DSMB make this determination. SafeHeal will notify all participating investigators, IRBs/Ethics Committees, FDA and other appropriate regulatory authorities of the termination of the investigation.

STATISTICAL ANALYSIS PLAN

CO-PRIMARY STUDY ENDPOINTS.

This study is intended to demonstrate the safety and effectiveness of the Colovac device using two co-primary endpoints. A closed testing method in which each of the primary endpoints specified below are compared using the full alpha will be used. Study success requires that the Colovac group successfully reject the null hypothesis for both of the individual primary endpoints. Because non-inferiority must be successfully shown for both endpoints for study success, the type I error rate is preserved at 5% for the entire primary endpoint.

As mentioned above, the primary study endpoint will consist of two individual co-primary endpoints, one safety and one efficacy measure. Specifically, the following endpoints are included as individual co-primary endpoints:

The primary safety endpoint is the rate of subjects with post-operative major complications within 12 months.

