The primary effectiveness endpoint for the Colovac-treated patients is: A clinically meaningful reduction in stoma creation rate

PRIMARY SAFETY ANALYSIS

The primary safety hypothesis is that the proportion of subjects with post-operative major complications within 12 months in the Investigational group is non-inferior to the proportion in the Control group using a 10% margin of non-inferiority. The hypotheses are as follows:

Definitions:

p_I : Proportion of subjects with postop major complications in the Investigational group.

p_C : Proportion of subjects with postop major complications in the Control group.

For the specified constant, $0 < \delta < 1$, the hypotheses of non-inferiority are:

$$H_0: p_I - p_C > \delta \text{ vs. } H_A: p_I - p_C \leq \delta.$$

The test will be based on the upper bound of a one-sided 95% confidence interval for the difference in proportions, Investigational minus Control. A conclusion of non-inferiority is supported if the upper bound of the confidence interval is <0.10 .

Non-inferiority Margin

This margin of $\delta=0.10$ is an appropriate value for the non-inferiority margin because the expected major complication rate in this study is approximately 40% for the Colovac group, and 48% for the Control group. As these rates have nearly the highest variance in the binomial distribution, use of a 10% margin is a reasonable choice per Chow and Song³⁹. This article mentions a “classical method” of determining the non-inferiority margin. As an example of a NI margin for a binary response (e.g. a success or failure rate), this method indicates that as a general rule, if the success rate is between 50% and 80% (failure rate between 20% and 50%), then a non-inferiority margin or equivalence limit of up to 20% could be chosen for non-inferiority trials. Although the expected major complication rate is approximately 40%, 10% was selected as a more conservative margin.

PRIMARY EFFICACY ANALYSIS

Study success will be defined as a clinically meaningful stoma reduction rate in the Colovac patients AND statistical non-inferiority on the primary safety endpoint (Colovac vs. Control). A benefit-risk assessment of all the clinical data will be performed to determine the ostomy reduction rate that balances the risk that device use may pose. This ostomy reduction rate will be considered clinically meaningful and provide the basis for the actual performance goal for this endpoint.

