Assuming a 40% vs 48% estimated rate of major complications in the Colovac treatment vs the standard of care arm, and a non-inferiority margin of absolute 10%, iterative simulation of the proposed adaptive design was performed to determine the maximum sample size and associated operating characteristics. This simulation showed that a maximum sample size of 342 randomized patients would produce 90% power under the expected device and control rates, assuming a 7% rate of loss to follow-up.

Regarding the Primary Efficacy Endpoint:

Study success will be defined as a clinically meaningful stoma reduction rate in the Colovac patients AND statistical non-inferiority on the primary safety endpoint (Colovac vs. Control). The clinically meaningful reduction in stoma creation is assumed to be 50%, which would require that more than half of all patients in the IDE Colovac group avoid an ostomy. Note that ostomy avoidance is expected in approximately 70% of Colovac patients and that, regardless of the final study results, the ostomy avoidance percent in the Colovac study group is expected to exceed 50% (lower limit of the 95% confidence interval of the point estimate). However, a benefit-risk assessment of all the clinical data will be performed to determine the ostomy reduction rate that balances the risk that device use may pose. This ostomy reduction rate will be considered clinically meaningful and provide the basis for the actual performance goal for this endpoint.

Assuming a success rate of 70% for the Colovac treatment, a total of 70 evaluable patients has 90% power to reject H_0 at a 2-sided $p<0.05$ significance level.

Total Sample Size:

Based on the primary endpoints, the larger sample size of 342 subjects was selected for the randomized component of the study. At least 50% of the randomized subjects will be enrolled at US sites.

The non-randomized run-in component will enroll up to 30 Colovac subjects (2 per site at up to 15 US sites) for a total of up to 372 subjects enrolled.

POPULATIONS FOR ANALYSIS

SAFETY POPULATION

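### Safety alpha, sample size and interim fraction do not agree: at the written one-sided 95% bound, 342 randomised gives about 94.5% power rather than 90%, and 140 patients is 41% of 342, not half

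*Combined protocol and SAP*

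**What the plan says.** Section 8.1.1 (Primary Safety Analysis) defines the test: "The test will be based on the upper bound of a one-sided 95% confidence interval for the difference in proportions, Investigational minus Control". Non-inferiority is concluded if that bound is below 0.10. Section 8.1 adds that "the type I error rate is preserved at 5% for the entire primary endpoint".

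Section 8.4 (Determination of sample size) assumes major complication rates of 40% (Colovac) and 48% (Control), a 10-point margin and 7% loss to follow-up. It says that "iterative simulation of the proposed adaptive design was performed to determine the maximum sample size and associated operating characteristics", and that "a maximum sample size of 342 randomized patients would produce 90% power under the expected device and control rates". It gives no alpha for that simulation. The only significance level named in Section 8.4 is two-sided 0.05, for the effectiveness endpoint.

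Section 8.4 calls 342 a maximum, but its total-sample-size paragraph treats it as the plan: "the larger sample size of 342 subjects was selected for the randomized component of the study". The Overall Study Design section says the same: "A total of 342 randomized subjects (171 investigational and 171 control subjects) will be enrolled". So does the Study Population section: "A total of 342 subjects (171 in the control arm and 171 in the Colovac arm) will be enrolled in the randomized component". The synopsis gives the same 171 + 171.

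Section 8.10 (Interim Analysis Specification) holds the interim when 140 patients have reached 12 months and calls this about half. It spends 0.001 of an overall 0.05 and leaves 0.049 for the final analysis. It does not stop the trial or reduce N. The independent statistician reports the N needed for 80% and for 90% power. If the initial n gives at least 80% power, nothing changes. Otherwise an increase may be requested, subject to FDA permission, with n_new = Max(n, n*).

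**The concern.** The final test, the sample size and the interim re-estimation should rest on one alpha and one total. Here the stated total and the stated interim count cannot both follow from the test in Section 8.1.1.

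Three things depend on this:

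- the power that the plan reports for its safety co-primary endpoint;
- the fraction of the trial on which N is re-estimated;
- the comparison of n with n*, because n* depends on alpha and on a power target that Section 8.10 does not fix.

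If the sponsor in fact meant one-sided 0.025, the criterion for declaring non-inferiority would also be stricter than the one now written.

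**Working it through.** **Inputs.** Rates 0.40 and 0.48, margin 0.10, 7% loss (Sections 8.1.1 and 8.4); 1:1 allocation (synopsis); interim at 140 patients and final alpha 0.049 (Section 8.10). The distance from the expected difference to the margin is 0.10 + 0.08 = 0.18. The unpooled variance sum is 0.40×0.60 + 0.48×0.52 = 0.2400 + 0.2496 = 0.4896.

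**Step 1: reproduce 342.** Per arm, n = (z(1−α) + z(0.90))² × 0.4896 / 0.18².

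| One-sided α | n per arm | Evaluable | Randomised (÷ 0.93) |
|---|---|---|---|
| 0.05 (as written) | 129.4 → 130 | 260 | 279.6 → 280 |
| 0.049 | 130.3 → 131 | 262 | 281.7 → 282 |
| 0.025 | 158.8 → 159 | 318 | 341.9 → 342 |
| 0.0245 | 159.6 → 160 | 320 | 344.1 → 345 |

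The stated 342 is matched exactly at one-sided 0.025. It is not matched at the written level.

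**Step 2: power of the written test at 342.** 342 × 0.93 ≈ 318 evaluable, or 159 per arm. Power = Φ(0.18 / √(0.4896/159) − z(1−α)) = Φ(3.244 − z(1−α)).

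- α = 0.05: Φ(1.599) = 94.5%
- α = 0.049: 94.4%
- α = 0.025: 90.0%
- α = 0.0245: 89.9%

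Exact binomial enumeration of the Wald bound agrees: 94.6% at both 0.05 and 0.049, and 89.8% at 0.025.

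**Step 3: interim fraction.** 140/342 = 40.9%; 140/318 = 44.0%; 140/280 = 50.0%. Half of 342 is 171, and half of 318 is 159.

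**Step 4: can the adaptive design account for 90%?** The Section 8.10 re-estimation was simulated at one-sided 0.05 with 70 evaluable per arm at the interim and n* computed from the observed rates. N was raised to n* but capped at 342 randomised (159 evaluable per arm). The cap is an assumption, since Section 8.10 states none.

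- Initial 280 randomised (400,000 runs per setting): power 94.0% if n* targets 80%, and 94.3% if it targets 90%.
- Initial sizes from 130 to 159 evaluable per arm: 93.9% to 94.7%.
- Initial 280 with no increase: 89.5% to 89.6%.
- The capped design at one-sided 0.025: 89.2% to 89.8%.

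At the written alpha, then, a figure near 90% appears only if N stays near 280.

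**Step 5: consequence for n*.** Take interim events of 31/70 (Colovac) and 34/70 (Control). The observed difference is −0.0429, so the distance to the margin is 0.1429, and the variance sum is 0.4965. For 80% power:

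- one-sided 0.05: 150.4 → 151 per arm, 302/0.93 → 325 randomised
- 0.049: 151.6 → 152 per arm, 304/0.93 → 327
- 0.025: 191.0 → 191 per arm, 382/0.93 → 411

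With n = 342, the first two mean no action. The third would add 411 − 342 = 69 patients.

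**Step 6: consequence for the final verdict.** With Control at 76/159, the largest Colovac count that passes (Wald bound) is 77 at 0.05, 77 at 0.049 and 74 at 0.025.

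**The case against.** The strongest reply is that 342 is the ceiling of an adaptive design, so a fixed-sample formula need not reproduce its power. Step 4 answers this. Raising N to n* under a cap of 342 gives about 94% at the written alpha, whatever the starting size in the range tried. One can get 89.7% by assuming that N rises only when n* fits within 342. But Max(n, n*) has no such exception, and the result is almost the power with no increase at all. It also needs an initial N near 280, which no section states and which contradicts every section that plans to enrol 342.

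Second, Section 8.4 says its aim is enough patients for at least 90% power on each endpoint, and 94.5% meets that aim. This stands. It limits the weight of the point, but it does not make 90% the right figure for the test as written.

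Third, Section 8.10 says only approximately half, and counts patients who have reached 12 months. The fairer denominator is therefore about 318 evaluable, which gives 44%. This narrows the gap but does not close it: half would be about 159.

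Fourth, a reader might infer that the increase rule is missing. It is not. Section 8.10 gives a trigger (below 80% power), a formula, a bar on reductions and an FDA condition. What it leaves open is the power target and the ceiling. The parenthesis at the 80% threshold suggests that n* is the 80% figure, yet both figures are reported and the increase aims at an unspecified desired power. Nor does the section say whether 342 limits n*.

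**Conclusion.** Sections 8.1.1, 8.4 and 8.10 do not agree, and at least one stated figure must change. With 342 as planned enrolment and the test as written, power is about 94.5% (94.4% at 0.049) rather than 90%, and the interim falls at 41% of randomised or 44% of expected evaluable patients. If 342 is only a maximum, the initial N is not given and the sections that plan to enrol 342 are wrong.

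The two-alpha explanation is an inference from exact matches (342 at one-sided 0.025; 140 as half of the 280 for one-sided 0.05). The power figures rest on the plan's own rates, margin and loss, and on an unpooled normal approximation confirmed by exact enumeration.

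Stronger readings are not supported:

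- A reader might infer that the trial is underpowered or that Type I error is inflated. At the written level the mismatch produces surplus power and does neither.
- A reader might infer that the interim cannot be run. It can be run at the written alpha: in the Step 5 example, n* is 325 or 327 and no action follows. The conflicting 411 needs one-sided 0.025, which no section states for safety.
- The failure to carry 0.049 into the Section 8.1.1 bound is a real inconsistency, but it moves power by 0.1 point and leaves the 77-event cut-off in Step 6 unchanged.

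This should be fixed, but it is a reconciliation of the plan and not a defect in the design.

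**What to change.** Amend the SAP wording before any unblinding:

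1. **One alpha.** State a single alpha for the safety test, the simulation and n*. If the written one-sided 5% test is kept, set the final bound at 0.049 (one-sided 95.1%) as Section 8.10 implies, and restate power at 342 as about 94%. If one-sided 0.025 was intended, change the bound in Section 8.1.1 and say that the test is stricter than the one now written. Power at 342 is then 90.0%, or 89.9% at 0.0245.
2. **Interim fraction.** Describe 140 patients as about 41% of 342 randomised (44% of expected evaluable). Alternatively, set the interim at about 159 patients reaching 12 months, or 171 if it is counted against randomised.
3. **Initial and maximum N.** State whether 342 is the initial or the maximum N, give the other value, and say which power (80% or 90%) defines n* and whether the maximum caps it. If 342 is only the maximum, correct the synopsis, the Overall Study Design and Study Population sections, and the total-sample-size paragraph of Section 8.4.

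**Cost.** Wording, plus a rerun of the existing simulation with its alpha and rules stated. Keeping the written test adds no patients. Choosing 0.025 makes non-inferiority harder to show, and a full 90% at 0.0245 would need 345 randomised (346 for equal arms). Raising the interim count delays it slightly. Assuming uniform accrual over the stated 8 to 12 months, 19 more evaluable patients take 19/318 of that period (0.5 to 0.7 months), and 31 more randomised patients take 31/342 of it (0.7 to 1.1 months).

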For study planning and sample size calculation purposes, the clinically meaningful reduction in stoma creation is assumed to be 50%, which would require that more than half of all patients in the IDE Colovac group avoid a stoma creation. Note that ostomy avoidance is expected in approximately 70% of Colovac

patients and that, regardless of the final study results, the ostomy avoidance percent in the Colovac study group is expected to exceed 50% (lower limit of the 95% confidence interval of the point estimate).

However, a benefit-risk assessment of all the clinical data will be performed to determine the ostomy reduction rate that balances the risk that device use may pose. This ostomy reduction rate will be considered clinically meaningful and provide the basis for a performance goal this endpoint.

Clinically Meaningful Reduction

The following factors will be considered in a Benefit-Risk assessment related to the ostomy avoidance rate.

The standard of care relies on the ostomy procedure to allow for anastomosis protection and decrease the need of a permanent stoma. Thus, by definition, the standard of care treatment would result in a stoma creation rate of 100%. As a result, a relatively small reduction in stoma creation is likely clinically meaningful. Additionally, we expect that the per-protocol use of Colovac will not result in a higher risk to subjects than the standard of care. However, as the clinical safety for Colovac has not yet been established, the potential risks and benefits of the Colovac and Control treatments are assessed.

The potential risks associated only with the use of the Colovac device in the IDE study are the risks related to a longer hospital stay, harm due to a failure of the device, risks from a later, more complicated ostomy surgery due to failure of the device, and the risks of late (> 10 days) AL and need for subsequent treatment. The potential risks associated with the standard of care, and potentially avoided by the use of Colovac, are the risks of ostomy, the stoma-related risks, the risks of stoma reversal and the risk of a significantly higher proportion of permanent stomas.

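### The pass mark for the co-primary effectiveness endpoint is not fixed: 50% is a planning value only, and nothing in the documents stops the actual goal being set after the stoma results are known.

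*Combined protocol and SAP*

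**What the plan says.** Section 8.1 requires both co-primary null hypotheses to be rejected and gives this as its ground for error control: "Because non-inferiority must be successfully shown for both endpoints for study success, the type I error rate is preserved at 5" percent.

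For safety, Section 8.1.1 writes out both hypotheses and fixes a 10% margin. For effectiveness, no hypotheses are written. The opening paragraph of Section 8.1.2 says how the required rate will be found: "A benefit-risk assessment of all the clinical data will be performed to determine the ostomy reduction rate". The section gives 50% only in this form: "For study planning and sample size calculation purposes, the clinically meaningful reduction in stoma creation is assumed to be 50" percent. It also expects about 70% avoidance and expects the lower 95% confidence limit to lie above 50%. It then qualifies this: "However, a benefit-risk assessment of all the clinical data will be performed to determine the ostomy reduction rate that balances the risk". On the result of that assessment it says: "This ostomy reduction rate will be considered clinically meaningful and provide the basis for the actual performance goal for this endpoint".

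The section headed Performance Goal for Primary Effectiveness and Section 8.4 say the same. The factors listed for the assessment are qualitative. In that list the plan remarks that "a relatively small reduction in stoma creation is likely clinically meaningful", and gives as a reason for weighing risks and benefits that "as the clinical safety for Colovac has not yet been established". Section 8.4 nevertheless states that "a total of 70 evaluable patients has 90% power to reject H_0" if the true success rate is 70%.

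**The concern.** A single-arm test against a goal controls error only if the goal is set without knowledge of the result. Here the planning value is expressly set apart from the actual goal. The documents do not say when the actual goal is chosen, by whom, from which data, or with what floor.

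The text allows this trial's own data to be used. The only earlier Colovac patient results described are the 15 SAFE-1 subjects, and the plan says that the device's safety is still to be established. Treatment is open-label and success is simply no stoma by 12 months, so no formal unblinding is needed to know the rate.

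The 10% safety margin protects against false success when the device is worse on safety. It does nothing when safety is acceptable and stoma avoidance falls short. In that case, success depends on a number that could be picked to suit the data, yet it would be reported as the outcome of a controlled test.

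**Working it through.** **Inputs.** Planning goal 50% (8.1.2, 8.4). Expected avoidance 70%, 70 evaluable patients, 90% power, two-sided 0.05 (8.4). 171 per arm and 7% loss to follow-up, so 171 × 0.93 = 159 evaluable. Safety rates 40% vs 48%, margin 10%, one-sided 95% limit (8.1.1, 8.4). SAFE-1 avoidance 10/15. Goals of 45% and 40% are assumptions used to show sensitivity.

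**1. Reproduce the plan's 70.** Use an exact binomial test with at most 0.025 in the upper tail and a true rate of 70%. Take the smallest n from which power stays at or above 90% for every larger n checked.

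| Null rate | n |
|---|---|
| 45% | 44 |
| 50% | **70** |
| 55% | 116 |

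At n = 70 the rule is at least 44 stoma-free, with upper-tail error 0.0207 and power 0.922. The stated 70 therefore rests on a 50% null.

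**2. Chance of passing effectiveness if true avoidance is 50%.** Success means that the lower limit of the exact (Clopper-Pearson) two-sided 95% interval exceeds the goal, with complete data. If k is the smallest passing count, the chance is P(X ≥ k) with X ~ Bin(n, 0.50).

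| Goal | k, n = 159 | Chance | k, n = 171 | Chance |
|---|---|---|---|---|
| 50% | 93 | 1.9% | 99 | 2.3% |
| 45% | 85 | 21% | 91 | 22% |
| 40% | 77 | 68% | 82 | 73% |

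For example, 86/171 stoma-free (50.3%) has a lower limit of 42.6%. It fails a 50% goal and passes a 40% goal.

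**3. Add the safety test.** Exact enumeration, Wald upper limit below 0.10, interim look ignored. At 40% vs 48% safety passes with probability 94.6% (n = 159 per arm) or 95.7% (n = 171). With pass probabilities a and b, the chance of passing both lies between max(0, a + b − 1) and min(a, b), whatever the correlation. For a 45% goal and n = 159 the lower bound is 0.214 + 0.946 − 1 = 0.160.

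| Goal | Study success, n = 159 | n = 171 |
|---|---|---|
| 50% | at most 1.9% | at most 2.3% |
| 45% | 16–21% | 18–22% |
| 40% | 63–68% | 69–73% |

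If safety is truly at the margin (58% vs 48%), the safety test passes 5.2% / 4.7% of the time, which caps study success near 5% whatever the goal.

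**4. Power if 50% is made binding.**

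| True avoidance | n = 159 | n = 171 |
|---|---|---|
| 70% | 99.9% | above 99.9% |
| 67% (SAFE-1) | 99% | 99% |
| 60% | 68% | 74% |
| 55% | 21% | 25% |

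The exact 95% interval for 10/15 is 38% to 88%.

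**The case against.** The best counter-reading is that 50% already works as a floor. Sections 8.1.2 and 8.4 say it would require more than half of Colovac patients to avoid a stoma, and that whatever the final results the lower 95% limit is expected to exceed 50%. That supplies a value, an interval and a direction. But it is worded as an expectation, both sections then turn to the benefit-risk assessment, and the remark about a small reduction being meaningful points to lower goals. It is not a binding criterion.

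Three other points have some force.

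- The documents never say that the goal will be set after the results. Other sources, such as the SH-001 cohort, the meta-analysis or the run-in subjects, could be meant. True, but a 5% claim requires that late setting be ruled out, and it is not.
- The pass rates above are for goals fixed at 45% or 40%. Passing a prespecified and justified 40% goal at a true 50% is power, not error. This stands: the table shows how strongly success depends on the goal. A goal chosen freely after the results has no defined error rate.
- A separate SAP may exist. The protocol cites it only for the goal of the secondary composite endpoint (Section 8.2), not for the primary one.

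**Conclusion.** The concern holds. As written, the plan does not deliver 5% error control for effectiveness, because the null value is not fixed and nothing in the documents requires it to be fixed before the stoma rate is known. The gap is limited to the case where safety is acceptable and effectiveness is not.

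In that case, at a true 50% avoidance, moving the goal from 50% to 40% raises the chance of study success from about 2% at most to between 63% and 73%. These figures assume complete data, an exact interval, the planned safety rates and no effect of the interim look. They are error rates only if 50% is the right bar. Because this is a co-primary endpoint of a pivotal trial and cannot be repaired once results are known, it must be fixed.

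**What to change.** In Sections 8.1.2 and 8.4, write H0: avoidance ≤ PG against HA: avoidance > PG for the Colovac ITT set, with a numeric PG. Fix it by dated amendment before anyone who sets or approves it has seen outcome data by arm. The natural value is 50%, which is already in the protocol and behind the 70 patients.

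Define success as the lower limit of the two-sided 95% interval for 12-month stoma avoidance exceeding the PG, combined across the multiple imputations that Section 8.5.2 requires, and name the interval method. Remove the sentences that let the benefit-risk assessment set the goal (Performance Goal for Primary Effectiveness, 8.1.2, 8.4). Keep that assessment as interpretation after the test.

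Two tidy-ups belong in the same amendment. Use one significance level for effectiveness: Section 8.4 has 0.05 and the tipping-point analysis in 8.7 has 0.049, though the passing counts above are the same at either. Correct Section 8.1, since effectiveness is a test against a goal and not a non-inferiority comparison.

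The cost is a formal amendment with approvals and the loss of freedom to move the goal. Sample size is unchanged because safety drives it. A binding 50% is a real choice: power is ample at 67–70% true avoidance but 68–74% at 60% and 21–25% at 55%, and SAFE-1 does not exclude those rates. If the sponsor thinks a lower goal is clinically justified, it can set one, but in advance and with reasons.
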